**F2. Procedure****RECRUITMENT**

A total of 200 child-parent dyads will be recruited through different methods. The primary sources will be through the TCH Autism Center, which sees at least 90 patients per month between the ages of 4-14 years with ASD, and through the Autism Center Research Database (ARCD), which has more than 1,700 families enrolled with the vast majority consenting to be recontacted for new study opportunities such as this one. Although it is anticipated that most of the study recruitment will occur through TCH Autism Center's normal patient flow and the ARCD, study advertisements will also be circulated through relevant sources (e.g., social media, websites, newsletters) to enhance enrollment and subject generality. As well, we will contact clinicians and professionals working with children with anxiety (e.g., private clinics, community organizations) to distribute advertisement flyers to potential participants. Interested potential participants will be asked to contact the research coordinator by email or telephone.

Recruitment will also be done through SPARK (Simons Foundation Powering Autism Research for Knowledge) which is a landmark autism research project with the mission of speeding up research and advancing the understanding of autism. SPARK's goal is to recruit 50,000 individuals in North America with a professional diagnosis of autism, and their family members, into an online research cohort. Approved researchers are allowed to recruit already enrolled SPARK families for additional studies. The Co-I, [name], and the study have been approved for recruitment through SPARK. Eligible SPARK participants will receive an invitation email with a link that directs them to an authorization page, where they can select yes or no to authorizing the research team to contact them. Three reminder emails are sent if there is no response. There are also 2 sequence reminders sent if families indicate interest but do not complete the authorization. When families authorize and provide contact information to reach them, SPARK will share their contact information with the research coordinator through a secure admin portal, giving her unique credentials to access it. Language for invitation email, reminder email, and authorization form can be found on section S.

#### INITIAL PHONE SCREEN.

Parents will be given a 20-minute telephone screening to elicit preliminary inclusion/exclusion information. Individuals who meet basic eligibility requirements during the phone interview and remain interested will be invited for a screening visit (i.e., baseline assessment), at which point a member of the research team will obtain informed consent from the parent and child.

#### INFORMED CONSENT

If and when a potential participant chooses to participate in this study, informed consent will be obtained. Participants will be provided with all relevant information and will be given as much time as needed to decide whether to participate. Participants will be informed that their participation or absence of participation will not have any influence on the clinical services received at TCH (or any other institution). Informed consent will be obtained prior to proceeding with any study procedures. All participants will also be informed that they do not have to answer any specific questions if they do not wish to do so. After obtaining consent, participants will complete the baseline assessment and begin treatment.

#### TREATMENT

All participants will receive parent-led, stepped-care cognitive-behavioral therapy (SC-CBT). CBT focuses on how a child's thoughts, beliefs, and attitudes affect feelings and behavior and teach children coping skills for dealing with different problems. The type of CBT that will be used is a specialized program for children and adolescents with ASD and comorbid anxiety. This type of treatment will be delivered using a stepped-care model, which provides therapy in "steps" that vary by intensity. Treatment is "stepped-up" until the child begins to show improvement in anxiety symptoms, beginning first with the lowest intensity (e.g., fewer in-person appointments, parent-led exposures) to more intensive (e.g., weekly in-person sessions, therapist-led exposures), as needed. SC-CBT consists of two main steps (detailed below). Each participant will be treated by a licensed psychologist/therapist or trainee under the supervision of a licensed psychologist. At the end of study participation, a standardized summary of assessment and treatment will be provided to research participants. Assessment summaries will contain information about inclusion criteria (e.g. SRS score, CSR score, PARS score, whether they met IQ cut off, etc.). It will be specified that this summary details research findings, and that our assessment is not equivalent or a substitution of a clinical evaluation. Treatment summaries will contain information about how many therapy sessions participants attended. Summaries will be reviewed and signed by PI before sharing them with research participants. Summaries will be shared through secure email, postal mail, or in person.

**STEP ONE.** All participants will start with Step One, which includes 4 parent-led, therapist-assisted sessions over a 12-week period. Parents will receive a parent-child workbook to use in session with the therapist, and at home. During each of these 4 sessions, the therapist will review with parents the necessary skills for conducting exposures and will provide guidance in the delivery of exposures. Exposures, a hallmark of CBT for anxiety are used to gradually and repeatedly confront feared stimuli. For example, exposure therapy for a child fearful of dogs may begin with looking at pictures of dogs and standing across the park from a dog on a leash, to eventually petting a dog. Outside of session, parents will lead therapy using the provided workbook, which consists of a step-by-step approach for parents written on a 6th-grade level. Brief phone contacts between parent and staff will also be provided for support, coaching, and motivation. After completing Step One, a brief assessment will occur (i.e., the mid-treatment). If the child meets treatment response status, then the parent and child end treatment and proceed to the Maintenance phase, where parents and children will be encouraged to continue using the workbook and tools that they learned in Step One. If the child does not meet treatment response (i.e., does not improve), then s/he will 'step up' to Step Two.

**STEP TWO.** For those children who do not respond to Step One, they will be 'stepped up' to Step Two, which consists of 10 therapist-led, parent-supported sessions, each lasting 60-120 minutes over the course of 12 weeks. During Step Two, therapists will lead exposure tasks and teach children response strategies. These strategies will focus on providing children with anxiety-coping skills. In addition, parents will be taught (in weekly sessions) to support children in learning and maintaining anxiety-coping skills, especially when outside of sessions. These skills are encouraged to be practiced at school, in the community, and in peer-group settings. After completing Step Two, participants will end treatment and the post-assessment will occur. For those participants in the maintenance phase (i.e., treatment responders at Step One), the post-assessment will occur approximately 12 weeks after the completion of the mid-treatment (for consistency with procedures in Step Two). All participants will then be re-assessed 3-months, after completion of the post-treatment.

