## Section D: Purpose and Objectives

The purpose of this study is to implement a parent-led, stepped-care cognitive behavioral therapy to children with ASD and anxiety. Specifically, we will (1) examine the effectiveness of Stepped-Care CBT (SC-CBT; e.g., starting with Step One parent-led, therapist-assisted treatment and then either maintenance or Step Two therapist-directed CBT), (2) examine the potential predictors of response to Step One that could be used as baseline tailoring variables to match children to the best level of care (i.e., Step One or CBT), and (3) examine the economic value of using a cost-effectiveness approach of SC-CBT. We expect that through Stepped-Care CBT, children’s anxiety levels will lessen.

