direct (e.g., cost of therapy session), indirect (e.g., travel costs, missed work), and opportunity costs (e.g., value of lost time; see above for cost measures). CEA often incorrectly omits the opportunity cost of patient/parent time spent on therapy, phone support, and at-home parent-child meetings. Non-study, mental-health service costs include inpatient, outpatient, and school-based services and will be priced using the Texas Medicaid fee schedules. Research-specific costs (e.g., screening, research consent) for patients and staff are excluded. Incremental cost-effectiveness ratios (ICER) are computed as incremental costs divided by incremental changes in morbidity/outcomes (symptom reduction and change in impairment/functioning). If outcomes differ significantly, a non-parametric bootstrap with replacement method is used to generate a joint distribution of differential costs and outcomes. If outcomes do not differ, cost-effectiveness is determined by examining treatment costs. Mean and median ICER ratios are reported, as well as 95% confidence intervals. Cost-effectiveness acceptability curves examine the probability of falling below a variety of cost-effectiveness thresholds. In addition to the ICER approach, the net-benefit approach will be used to determine if findings are sensitive to method.

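### The cost-effectiveness effect in G2 has no time weighting and no stated horizon, so the 12-week later start of therapist-led CBT for stepped-up children may carry no weight in it

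*Combined protocol and SAP*

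**What the plan says.** **Timing (F2, Treatment).** The protocol states: "All participants will start with Step One, which includes 4 parent-led, therapist-assisted sessions over a 12-week period". Response is judged at the end of that period: "After completing Step One, a brief assessment will occur (i.e., the mid-treatment". No earlier step-up is described. Non-responders go to Step Two, "which consists of 10 therapist-led, parent-supported sessions, each lasting 60-120 minutes over the course of 12 weeks". For Step One responders, "the post-assessment will occur approximately 12 weeks after the completion of the mid-treatment". Then: "All participants will then be re-assessed 3-months, after completion of the post-treatment". The schedule is therefore Step One in weeks 0–12, Step Two or maintenance in weeks 12–24, and follow-up at about week 36.

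**Economic aim (Section D).** The third aim is to "examine the economic value of using a cost-effectiveness approach of SC-CBT".

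**Economic analysis (G2).** SC-CBT is compared with CBT from a societal perspective. ICERs are "computed as incremental costs divided by incremental changes in morbidity/outcomes (symptom reduction and change in impairment/functioning". If outcomes differ significantly, a bootstrap of costs and outcomes follows. Otherwise, "If outcomes do not differ, cost-effectiveness is determined by examining treatment costs". A net-benefit analysis is added, with no separate effect measure. G2 states no assessment time or horizon for the effect, and names no area under the curve, symptom-free time or QALY.

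**The concern.** Stepped care offers a cheaper first step to everyone. In exchange, therapist-led care starts later for those who turn out to need it. An economic evaluation of stepped care should be able to show both sides of that exchange. The cost side of G2 is detailed and even counts parents' time. The effect side is a change in score, which records how far a child improved but not how long the child stayed unwell first.

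If the two strategies reach similar scores, the effect difference is near zero, the cost-only rule applies, and the cheaper strategy is preferred. The extra weeks of symptoms among stepped-up children then have no part in the effect comparison. The protocol itself treats time as important: Section C says that untreated anxiety tends to get worse, and Section I counts quicker access to treatment as a possible benefit of taking part.

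**Working it through.** The plan gives no figure of its own to reproduce here. The check asks what a change score and a time-weighted score each show for the same pair of courses.

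**Inputs from the documents:** 12 weeks of Step One; 12 weeks of Step Two; follow-up 3 months later (taken as about 12 weeks); ratings at baseline, mid-treatment, post-treatment and follow-up (F1).

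**Assumed, because the documents give no values:** the full gain D in points; the share f of it that a stepped-up child gains during Step One; the proportion p stepped up; direct CBT that starts at week 0, improves linearly over 12 weeks and holds; equal end scores; and Step One responders who do as well as with direct CBT.

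**1. Change score.** At week 24 or week 36 both courses show D, so the difference is D − D = 0. It is also 0 if direct CBT is read at week 12 and SC-CBT at week 24, each at its own end of treatment.

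**2. Area of benefit, weeks 0–36, trapezoid rule.**
- Direct CBT: ½ × 12 × D + 24 × D = 30D.
- Stepped-up child: ½ × 12 × fD + ½ × 12 × (fD + D) + 12 × D = 18D + 12fD.
- Loss: 30D − 18D − 12fD = 12D(1 − f) point-weeks.
- Share of direct-CBT benefit: 12D(1 − f) / 30D = 0.4(1 − f), whatever D is.

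**3. Numbers for an assumed D = 6 (direct CBT: 30 × 6 = 180 point-weeks).**

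| f | Stepped-up area | Loss (point-weeks) | Mean loss over 36 weeks | Share of direct benefit |
|---|---|---|---|---|
| 0 | 108 | 72 | 2.0 points | 40% |
| 0.25 | 126 | 54 | 1.5 points | 30% |
| 0.5 | 144 | 36 | 1.0 point | 20% |

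**4. Cohort average, p × 0.4(1 − f).** For p = 0.3, 0.5 and 0.7 the loss is 12%, 20% and 28% at f = 0, and 6%, 10% and 14% at f = 0.5.

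**5. Sensitivity to the horizon.** Over weeks 0–24 direct CBT gives ½ × 12 × D + 12 × D = 18D. The loss is still 12D(1 − f), so the share becomes 67% at f = 0 and 33% at f = 0.5. The same delay looks quite different under two horizons, and G2 fixes neither.

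**6. Sensitivity to the length of CBT.** If direct CBT takes 16 weeks, with D = 5 and f = 0, its area is ½ × 16 × 5 + 20 × 5 = 140 against 18 × 5 = 90. The loss is 50 point-weeks, or 50/140 = 36%.

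**The case against.** The strongest reply is that G2 never says when the effect is read. A reader might infer that the effect is a baseline-to-end difference that cannot show delay, and that the ICER is therefore biased toward SC-CBT. The text does not go that far. On the courses above, a comparison at week 12 would set D against fD and show the delay in full. This stands as a limit on the claim. It does not remove the point, because Step Two has not begun at week 12, so a reading then would not evaluate the stepped strategy. At any reading from week 24 on, equal scores give zero.

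The second reply concerns the comparator, and it stands. All participants receive SC-CBT (F2), and no source of CBT outcomes or costs is named. Section I mentions the usual clinic wait list, so a week-0 start for CBT is itself an assumption. If direct CBT started w weeks later (w up to 24), its area would be (30 − w)D and the loss would fall to D × [12(1 − f) − w]. A reader might also infer that the problem is the same whatever supplies the CBT data. That is too strong: the missing source is a prior gap, and no delay can be valued until it is filled.

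Third, societal costs such as missed work and other mental-health services may pick up part of the delay. This stands in part. They do not measure the child's symptom burden, and the fallback rule refers to treatment costs, whereas G2 lists non-study services separately.

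Fourth, Step One is active, therapist-assisted exposure work, so f may be well above 0. This stands, and it is why the result is given as a range. Finally, the list of measures is in attachments not available here, so relevant detail may exist there.

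**Conclusion.** The point holds in a conditional form. The effect in G2 is an unweighted change with no stated reading time or horizon. If it is read at about week 24 or later, or at each strategy's own end of treatment, the extra symptom burden of stepped-up children has no weight on the effect side, and the cost-only rule can then favour SC-CBT.

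Under the stated assumptions, what goes uncounted is 20–40% of the direct-CBT benefit over 36 weeks per stepped-up child, for f from 0.5 to 0. The percentages do not depend on D, but they do depend on the assumed course, the week-0 start of CBT and the 36-week horizon. They illustrate scale and are not estimates for this trial. If Step One responders do better or worse than under direct CBT, the cohort figure changes too. The documents do not establish that the ICER will be biased in a known direction.

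**What to change.** In G2:

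1. Name the source of the CBT comparator's outcomes and costs. The steps below depend on it.
2. Set one horizon for costs and effects, from baseline to the 3-month follow-up (about 36 weeks), for SC-CBT and for whatever CBT comparator is used.
3. Report a time-weighted anxiety effect alongside the change score in the ICER and net-benefit analyses: the trapezoid area under the severity curve from the four planned assessments at their actual dates. Confirm that the same anxiety scale is used at all four.
4. Apply the cost-only rule only if the time-weighted effect also does not differ.
5. Do the same for impairment only if it is rated at mid-treatment. That visit is described as brief, and the documents do not show that impairment is rated there.

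This needs no new visits or participants, only plan wording and modest programming. The downsides are interpolation between four ratings, a possibly less favourable result for SC-CBT, and the need for comparator scores by time. Mean scores by time are enough for a mean area. If the CBT source has only pre- and post-treatment summaries, the curve must be modelled and the plan should state how.

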#### ASSESSMENTS

All participants will be asked to cooperate in assessments that will occur as described above. All assessments will be conducted with an independent evaluator (IE). The IE will be an experienced clinician, trained professional, or advanced graduate trainee (supervised by a clinician). The measures that will be administered will include both IE-rated and participant-rated scales (please see attachment in section S). To reduce burden for families, post-assessment and 3-month follow-up measures will be completed through a secure connection using video-conferencing software (Zoom). Zoom is a secure HIPAA-compliant video-conferencing software.

In addition to completing rating scales, participants will be asked to participate in several objective assessment tasks, examining physiological and motor characteristics. These tasks will be given at baseline and at post-treatment, and will measure the participants gait performance (e.g., gait speed) and balance (e.g., center of mass sway). Both gait performance and balance will be assessed on-site during the in-person visits through the use of wearable sensors. Sensors transmit data to a BCM encrypted laptop via Bluetooth function (wireless), and data are saved in the laptop automatically. The sensor data will not include identifiable information such as name and date of birth. We will use HIPAA compliant BCM Box for transmitting the collected data and for storage. Data collected for each participant will be coded to ensure confidentiality. Only study personnel will have access to subjects' records. Data may also be shared with study's co-investigators (on this IRB protocol) through BCM Box. However, data that could in any way identify subjects will not be made public or shared. All of the outcomes in these tasks will be measured using previously validated wearable sensors (more information attached in section S).

#### TREATMENT FIDELITY/INTEGRITY

All clinician and assessment sessions, in both conditions, will either be audio-recorded or video-recorded (with parent consent). These recordings will be used for research purposes, to monitor ongoing fidelity in Steps One and Two, to quantify treatment adherence, as well as to assess the inter-rater reliability and rater drift. If concerns are noted, the clinician and/or IE will not conduct another assessment until procedures have been reviewed. Clinicians will upload recordings to a web-secure, HIPPA-compliant storage (Box). Fidelity measures have been developed in our pilot work and adapted for use in this project: [1] The Parent Completion and Effort Rating (PCER); [2] The Adaptation Checklist-Child; [3] The Step One Treatment Checklist; [4] The Treatment Adherence, Content, and Competence Checklist.

#### TEMPORAL CHANGES DUE TO COVID-19

Please see procedural changes due to COVID-19 attached in Section S (due to limited remaining characters)

### Section G: Sample Size/Data Analysis

#### G1. Sample Size

How many subjects (or specimens, or charts) will be used in this study?

Local: 200      Worldwide: 200

Please indicate why you chose the sample size proposed:

We will enroll a total of 200 participants, which achieves sufficient power for the primary and secondary aims. Although we expect slight attrition, the below-mentioned analyses allow for attrition without the loss of data. While MLM does not provide for specific power analyses, the suggested power rules range from 20 participants per group, per level. As such, to be conservative with our power estimates, we aim to enroll 200 participants to ensure we are sufficiently powered for our analyses, accounting conservatively for attrition (~7% at Step One; ~15% at Step Two).

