#### G2. Data Analysis

Provide a description of your plan for data analysis. State the types of comparisons you plan (e.g. comparison of means, comparison of proportions, regressions, analysis of variance). Which is the PRIMARY comparison/analysis? How will the analyses proposed relate to the primary purposes of your study?

Data analysis will involve Multilevel Modeling (MLM) because of the *nesting* nature of the variables. More specifically, because the measures are repeated, the measures are considered the first level of the hierarchy, the individual children are considered the second level, and the treatment groups are considered the third level. A major advantage of MLM is its ability to handle missing data. While more traditional analyses use listwise deletion if a single time point is missing, MLM uses parameter estimates to maximize the use of existing data. Furthermore, the present study will implement a regression discontinuity analysis, which is an application of mixed models within MLM. This will allow us to examine the impact of treatment, without the use of random assignment, as this method allows for the use of groups that are similar at baseline, but then are designated by a predetermined selection cut point.

After assessing responder status and determining which participants receive Step Two treatment and which participants move to the maintenance phase, binary logistic regression will be utilized in an attempt to determine if there are factors significantly predicting group membership. Possible predictors include variables such as age, anxiety severity, internalizing/externalizing problems, and parent characteristics.

Cost-effectiveness analysis examines the relative value of SC-CBT (relative to CBT). CEA is performed from a societal perspective, meaning the costs to the healthcare system and the patient/parents are included. Treatment costs include

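### G1 claims sufficient power for the aims, but the design holds no CBT data for the SC-CBT versus CBT contrast, and the head-count rule does not support the claim for the regression discontinuity

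*Combined protocol and SAP*

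**What the plan says.** G1 makes a general claim: "We will enroll a total of 200 participants, which achieves sufficient power for the primary and secondary aims". It justifies the number by a rule of thumb: "While MLM does not provide for specific power analyses, the suggested power rules range from 20 participants per group, per level". It then says that 200 was chosen "to ensure we are sufficiently powered for our analyses, accounting conservatively for attrition (~7% at Step One; ~15% at Step Two"). It gives no significance level, target power, effect size, variance, visit correlation or response rate.

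Section D lists three aims without ranking them: effectiveness of SC-CBT, predictors of Step One response, and economic value. The third is to "examine the economic value of using a cost-effectiveness approach of SC-CBT". G2 gives that aim a comparator: "Cost-effectiveness analysis examines the relative value of SC-CBT (relative to CBT"). G2 also makes the economic method depend on an outcome test: "If outcomes differ significantly, a non-parametric bootstrap with replacement method is used", but "If outcomes do not differ, cost-effectiveness is determined by examining treatment costs".

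F1 and F2 (Treatment, Step One, Step Two) describe one pathway. Every child receives SC-CBT and begins with the parent-led Step One. Only children who do not respond at mid-treatment go on to the therapist-led Step Two. G2 also plans an RD at the cut point that divides these two routes.

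**The concern.** A power claim for the aims should hold for the contrasts that those aims need. One of them, SC-CBT against CBT, has no children on one side. Another, the RD, loses precision in a way that a head count cannot show.

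Two misreadings are at stake. The cost result could be taken as a powered comparison with CBT, although no child receives CBT from the start. A null RD result could be reported as adequately powered and showing no effect, although the plan gives no detectable effect for it.

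**Working it through.** **1. The plan's own rule.** G2 describes three levels (measures, children, treatment groups), and the design yields two groups after Step One (maintenance and Step Two).
- 20 × 2 × 3 = 120.
- Allowing for 7% loss: 120 / 0.93 = 129.03, so 130.
- Allowing for both losses: 120 / (0.93 × 0.85) = 151.8, so 152.

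So 200 exceeds the rule on this reading and is not an arithmetic error. G1 calls it a conservative choice. But the rule contains no effect size or variance, so no power figure can be reproduced from it.

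**2. SC-CBT versus CBT.** The variance of a difference in means is σ²(1/n_SC + 1/n_CBT). Here n_SC is at most 200 and n_CBT = 0. The second term is undefined, and raising n_SC does not change that. The significance test in G2 that selects the economic method needs the same contrast, so it cannot be run either.

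Step Two children cannot fill the gap. Section D does use CBT for the therapist-directed level, where it speaks of predictors that could "match children to the best level of care (i.e., Step One or CBT"). But children reach that level only after Step One has not worked for them, so they are a selected group who have already had treatment. They do not show what CBT from the start would cost or achieve.

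**3. Regression discontinuity.** The assumptions, none of them in the documents, are a normal running variable, a linear fit and a proportion s stepping up of 30% to 70%. The squared correlation between the step indicator and the running variable is ρ² = φ(z)² / [s(1 − s)], where z is the normal quantile of s. The variance inflation against a randomised comparison with the same split is 1 / (1 − ρ²).
- s = 50%: ρ² = 0.1592 / 0.25 = 0.637, inflation 2.75.
- s = 30% or 70%: ρ² = 0.1209 / 0.21 = 0.576, inflation 2.36 (common slope).

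To show what this does, take two-sided 5%, 80% power (multiplier 2.80), 50% stepping up, and the 15% loss confined to Step Two.
- After Step One: 200 × 0.93 = 186, or 93 on each route.
- At post-treatment: 93 in maintenance and 93 × 0.85 = 79 in Step Two, 172 in all.
- Ordinary two-group detectable difference: 2.80 × √(1/79 + 1/93) = 0.43 SD.
- RD, no covariate gain: 0.43 × √2.75 = 0.71 SD.
- RD, residual variance halved by covariates: 0.71 × √0.5 = 0.50 SD.

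In simulations at a true effect of 0.5 SD (2,000 trials per setting, 30% to 70% stepping up, visit correlation 0.5 to 0.7), RD power ran from about 41% to about 96%. The low end uses change from baseline as the running variable with no baseline covariate. The high end uses a baseline covariate, averages post-treatment and follow-up, and assumes a sustained effect with no further loss. The plan does not say which of these models applies.

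**4. Multilevel models and power.** A detectable effect for a repeated-measures model follows from n and the visit correlation, or from simulation. The G1 statement that such models do not provide for power analyses is therefore incorrect.

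**5. Where 200 is not in doubt.** With 200 × 0.93 × 0.85 = 158 completers, a within-child change of 2.80 / √158 = 0.22 SD of the change score is detectable. For the predictor aim, 186 children and one predictor per SD give exp(2.80 / √(186 × 0.25)) = 1.51 as the detectable odds ratio at a 50% response rate. At 30% or 70%, with R² = 0.3 with the other predictors, it is exp(2.80 / √(186 × 0.21 × 0.7)) = 1.71. These are illustrations on the same assumed error rates.

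**The case against.** The strongest reply is that G1 discusses only multilevel modelling, so the analyses it calls powered may be the multilevel ones. The third aim in Section D mentions no CBT contrast; that enters only in G2. On this reading G1 is silent about SC-CBT versus CBT rather than wrong. The reading is possible, but it does not remove the problem. The first sentence of G1 refers to the aims, the cost aim is one of three, and G2 still states a decision rule that cannot be applied.

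Some material is not visible. Measures and COVID-19 changes are sent to Section S, and the cost-effectiveness text refers back to cost measures that do not appear in the form. A response definition or a cost source may sit there. This limits certainty, but G1 cites no attachment for power and the cost-effectiveness text names no CBT data. The reference to two conditions under treatment fidelity, read in context, means Steps One and Two and adds no arm.

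It is also fair that the RD part shows no error, only a missing detectable effect. A reader might infer from the inflation factor that the RD is underpowered, or that 200 is too few overall. The documents support neither inference. The running variable, cut point, response rate and model form are not given, and under some choices power at 0.5 SD would be high.

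**Conclusion.** The point holds in three parts of different strength.

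- **SC-CBT versus CBT: wrong as written.** With no CBT children and no named outside source, the contrast has no power at any sample size, and the significance-based switch cannot be run. This rests on the design text alone and needs no numerical assumption.
- **RD: unsupported, not shown false.** The variance inflation of about 2.4 to 2.8 depends on the assumed normal running variable, linear fit and 30% to 70% stepping up. The head-count rule does not reflect any such loss.
- **The statement about multilevel models and power: incorrect.**

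For cohort change and the predictor aim, G1 lacks a detectable effect, but nothing shows that 200 is too small. This is a fault in the design and the power statement, not in the arithmetic. It should be corrected before results are interpreted.

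**What to change.** In G1, remove the blanket power claim and the sentence about multilevel models. State that the study is not powered for SC-CBT versus CBT.

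In G2, make the cost aim descriptive and remove the switch based on whether outcomes differ, unless a CBT data source is named. If one is named, give the detectable difference from both sample sizes.

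For the RD, report a detectable effect from the sponsor's own simulation, using the actual running variable, cut point, response rate and attrition by step. Without it, do not describe a null RD result as adequately powered.

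The figures under the working are illustrations and should not be copied into the protocol as detectable effects. No change to the sample size is requested, in either direction. The cost is one short simulation and some rewritten text, and the stated power will look less favourable.
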